### **Statistical Considerations**

Primary outcomes: Neural activity and self-reported feelings of connection in response to the messages task and the picture-viewing task.

Neuroimaging outcome: The imaging data will be analyzed using SPM8 (Wellcome Department of Cognitive Neurology, Institute of Neurology, London, UK). Images for each participant will be realigned to correct for head motion, normalized into a standard stereotactic space, and smoothed with an 8mm Gaussian kernel, full width at half maximum, to increase signal-to-noise ratio. The imaging tasks are all block designs and therefore we will use a boxcar function convolved with a canonical hemodynamic response function. For each participant, each block

type will be modeled separately (e.g. viewing images of a close other will be modeled separately from viewing images of a stranger). After the task is modeled for each participant, planned comparisons will be computed as linear contrasts to investigate neural activity separately during each of the conditions compared to baseline (fixation crosshairs) and each condition compared to its respective control condition (e.g. images of close other vs. images of stranger). Random effects analyses of the group will be computed using the contrast images generated for each participant.

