To assess between-group differences in the effect of naltrexone vs. placebo on neural responses to the different tasks, we will conduct two kinds of analyses for each task. First, based on a priori hypotheses regarding the effect of naltrexone on affiliation-related neural responses, we will conduct region-of-interest (ROI) analyses, using structurally-defined ROIs, to examine between-group differences in neural activity in these pre-specified neural regions ( $p < .05$ , corrected). For the task where participants read messages from their loved ones, ROIs of the VS and mid-insula, have been created (with the PickAtlas toolbox) using the automated anatomical atlas (AAL; Tzourio-Mazoyer et al., 2002), and will be examined to see if average neural activity in these regions differs between naltrexone and placebo participants in response to the messages. Similarly, for the picture-viewing task, ROIs of the left and right VS will be analyzed in the same way (these have also been structurally defined previously; Inagaki et al., 2015). Second, to more fully investigate the specific neural regions that are differentially activated as a function of naltrexone (beyond the predicted ROIs), we will conduct whole-brain between-group analyses to see which neural regions differ in activity among participants exposed to naltrexone vs. placebo ( $p < .001$ , 10 voxels).

Feelings of social connection: To assess between-group differences in the effect of naltrexone vs. placebo on self-reported feelings of connection in response to the scanner tasks, we will conduct independent samples t-tests.

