## Results for primary outcomes

Effect of Naltrexone on Neural Activity to Messages task: To examine the effect of naltrexone on neural activity to the social warmth task, analyses were constrained to the a-priori defined VS and MI mask. VS and MI activity was greater to messages from close others than strangers (*left*  $t(76)=6.138$ ,  $p < .001$ ; *right*  $t(76)=4.493$ ,  $p < .001$ ). Naltrexone, however, reduced VS and MI activity to the social warmth task as compared to placebo (*left*  $t(75)=1.859$ ,  $p=.034$ ; *right*  $t(75)=2.198$ ,  $p=.016$ ).

Effect of Naltrexone on Feelings of Social Connection to Messages task: The effect of drug on feelings of social connection to the messages task was in the expected direction, but did not reach statistical significance ( $p > .10$ ).

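### The plan requires corrected ROI tests of a difference, but the reported drug effects are one-sided, uncorrected p-values; two-sided and corrected over the two hemispheres, neither meets .05

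*Combined protocol and SAP*

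**What the plan says.** The Statistical Considerations section of the combined protocol and SAP lists the co-primary outcomes: "Primary outcomes: Neural activity and self-reported feelings of connection in response to the messages task and the picture-viewing task".

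For the imaging outcome it plans ROI analyses "to examine between-group differences in neural activity in these pre-specified neural regions", with the threshold set at p below .05 after correction. The regions for the messages task "will be examined to see if average neural activity in these regions differs between naltrexone and placebo participants". That wording is non-directional, and the quantity tested is a regional average. For the messages task, "ROIs of the VS and mid-insula, have been created". For the other task, "for the picture-viewing task, ROIs of the left and right VS will be analyzed in the same way".

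The section does not say which correction applies, over which tests, or whether tests are one- or two-sided. For the messages task it also does not say whether VS and mid-insula (MI) are tested separately or together, or by hemisphere.

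The results section states that "analyses were constrained to the a-priori defined VS and MI mask". It then gives one drug-effect statistic per hemisphere: left t(75)=1.859, p=.034; right t(75)=2.198, p=.016. It concludes that naltrexone lowered activity in both VS and MI. It mentions neither a correction nor a one-sided test.

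**The concern.** The two imaging p-values are the only positive drug effect in the document; the self-report result for the same task is reported as non-significant (p > .10). Read as printed, both look comfortably below .05. The plan, however, set a corrected threshold, and nothing in the results indicates that a correction was made. A regional average yields one test per region and side, so there are no voxels within the region to correct over. The natural reading is therefore correction across the ROI tests.

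If the printed values are uncorrected, the headline claim has not been tested against the plan's own rule. If they are also one-sided, a reader who assumes the usual two-sided test will take them at half their size. A related problem is that the conclusion names two regions but rests on one number per side.

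**Working it through.** **Inputs** (results section): left t=1.859, right t=2.198, both with 75 df; reported p .034 and .016. From Statistical Considerations: level .05, corrected.

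**1. Reproduce the reported values.** One-sided p = P(T > t) with T on 75 df.
- Left: P(T > 1.859) = .0335, reported .034. Because t is itself rounded, the true value lies between 1.8585 (p=.03351) and 1.8595 (p=.03344), so .034 is consistent.
- Right: P(T > 2.198) = .0155, reported .016.

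The alternatives do not fit. Two-sided uncorrected values would be .0669 and .0310. One-sided Bonferroni over two tests gives the same pair. The printed figures are therefore one-sided and uncorrected.

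**2. Two-sided, uncorrected.** p = 2 × one-sided.
- Left: 2 × .0335 = .067. This exceeds .05 before any correction.
- Right: 2 × .0155 = .031.

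**3. Two-sided, corrected over the two reported hemispheres (m = 2).**

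| Method | Left | Right |
|---|---|---|
| Bonferroni, 2 × p | .134 | .062 |
| Sidak, 1 − (1 − p)² | .129 | .061 |
| Holm: smaller p × 2, then the larger of that and the other p | .067 | .062 |

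The two-sided Bonferroni critical value is the 1 − .0125 quantile of t on 75 df, 2.287. The larger observed value is 2.198.

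**4. One-sided, corrected over the same two tests.**

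| Method | Left | Right |
|---|---|---|
| Bonferroni | .067 | .031 |
| Holm | .0335 | .031 |

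The right side survives under both methods, and the left under Holm only.

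**5. Allowing for correlation between hemispheres.** The documents do not give this correlation, so it is an assumption shown over a range. The adjusted two-sided p is the simulated probability that the larger of two correlated |t| values on 75 df exceeds the observed one.

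| Assumed correlation | Right, adjusted p |
|---|---|
| 0 | .061 |
| .5 | .057 |
| .7 | .053 |
| .8 | .049 |
| .9 | .044 |

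The right side falls below .05 only at a correlation of about .8 or more. The left single-step value is still .085 at .95, and no adjustment can take it below its unadjusted .067.

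**6. Regions.** The plan lists VS and MI. The results give one t per side for a mask described as containing both. A single statistic per side could arise from an effect in either region alone, so it does not by itself establish an effect in each.

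**The case against.** The best defence concerns sidedness. The plan never states it. The ROI section refers to a priori hypotheses, and the Scientific Background suggests that opioid antagonism may lower activity in affiliation-related regions. If one-sided testing is accepted, Holm over two hemispheres keeps both effects and Bonferroni keeps the right. This stands as a limit on the conclusion. It does not rescue the report as written, because neither a one-sided test nor a two-test family was declared, and the planned question is whether activity differs.

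It is also fair that Bonferroni and Holm ignore correlation between hemispheres. A high enough correlation would bring the right side under .05, as shown above, but would not help the left.

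A third objection is that pooling VS and MI may have been intended: the results call the mask a priori, and the plan is silent on pooling for this task. That is right. Pooling is inferred from the single mask and the single t per side, and is not shown to be a departure. The limit on what one statistic can say about two regions remains.

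Three stronger readings are tempting and are not supported:
- **Larger multipliers.** A reader might count every listed ROI and side across both tasks and multiply the printed p-values accordingly. Separate VS and MI statistics and the picture-task results are not reported, so combined-mask p-values cannot stand in for them.
- **Self-report inflation.** A reader might count the example rating items as separate tests. They are given only as examples, no item-level testing is planned, and the messages-task self-report result is reported as non-significant.
- **A probable false positive somewhere.** The documents give neither the number of tests nor their dependence, so no such probability can be computed.

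**Conclusion.** The concern holds. The reported drug effects on messages-task activity are one-sided and uncorrected, neither fact is disclosed, and the plan calls for correction. This follows directly from the printed t-values and needs no assumption.

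That neither effect meets .05 after correction (.134 and .062 by Bonferroni; .067 and .062 by Holm) rests on two assumptions: two-sided testing, which the plan's wording implies but does not state, and a family of the two reported hemispheres. For the right side it rests also on a correction that ignores between-hemisphere correlation. The left side fails two-sided under any correction.

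A reader might infer that the drug effect has been shown to be absent, or that it would fail in each region once properly tested. The documents do not support that. The separate regional results have not been reported and could be stronger or weaker than the combined ones.

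**What to change.** In Statistical Considerations, state that ROI tests are two-sided, with Holm correction across the listed ROI tests within each task: VS and MI by side for messages, left and right VS for pictures. Because results already appear in the document, mark this as specified after they were known.

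In the results section, label .034 and .016 as one-sided and uncorrected. Beside them give the two-sided values (.067, .031) and the Holm values over the two reported tests (.067, .062).

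Then report VS and MI separately by side from the existing images and masks, with p-values adjusted over that family, and word the drug-effect conclusion according to what those results show.

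The cost is a few sentences of SAP text, a small re-extraction and a revised results paragraph. No new data are needed. The downside for the sponsor is less favourable p-values than those now printed.

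### The whole-brain drug comparison (p < .001, 10 voxels) has no family-wise correction; depending on unstated image settings, its false-cluster risk runs from about 5% to near certainty

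*Combined protocol and SAP*

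**What the plan says.** Under Statistical Considerations the plan announces that "we will conduct two kinds of analyses for each task". The two kinds have different error standards.

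- **ROI analyses.** The aim is "to examine between-group differences in neural activity in these pre-specified neural regions ( $p < .05$ , corrected"), so a correction is stated, though its type is not.
- **Whole-brain analyses.** The aim is "to more fully investigate the specific neural regions that are differentially activated as a function of naltrexone (beyond the predicted ROIs"). To that end "we will conduct whole-brain between-group analyses to see which neural regions differ in activity among participants exposed to naltrexone vs. placebo", and the threshold given in parentheses is p < .001 with 10 voxels. No family-wise, false-discovery or cluster-level qualifier is attached, and no derivation of the 10-voxel extent is given.

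The only smoothness figure is that images are "smoothed with an 8mm Gaussian kernel, full width at half maximum". The first-level contrasts include each condition against baseline and "each condition compared to its respective control condition". The plan does not say which of them go into the whole-brain drug comparison. Voxel size after normalization, effective smoothness, search mask and sidedness are not stated. Neural activity is named among the primary outcomes, and nothing marks the whole-brain search as exploratory.

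**The concern.** The search with by far the most comparisons has the weaker stated control. An extent rule limits false clusters only if the extent is large relative to the smoothness of the noise, and a count of voxels means nothing until the voxel size is known. Ten voxels is 10 × 2³ = 80 mm³ at 2 mm, 10 × 3³ = 270 mm³ at 3 mm and 10 × 4³ = 640 mm³ at 4 mm. A cube with the side of the applied kernel is 8³ = 512 mm³. At 2 or 3 mm the rule therefore asks for less than one smoothing element, which smoothed noise can supply; at 4 mm it asks for slightly more than one.

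What is at stake is the regional claim. The purpose of the search is to name further regions altered by naltrexone, and without a correction or a label a reader could take any such region as a drug effect.

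**Working it through.** The plan gives no family-wise error rate or derivation for the 10-voxel extent, so there is no figure of its own to reproduce. The check is the chance, with no drug effect anywhere, of at least one cluster of 10 or more voxels at p < .001.

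**Inputs from the documents.** Voxel p < .001 and extent 10; 8 mm applied kernel; two tasks; 75 error degrees of freedom, from the t statistics under Results for primary outcomes. The one-direction threshold is then t = 3.20.

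**Assumptions.** Isotropic voxels of 2, 3 or 4 mm; effective smoothness (FWHM) of 8 to 14 mm; search volume V = 1.5 litres, with 0.8 to 1.8 litres as sensitivity; a sphere for the brain.

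**Random field formulas.**

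1. Expected number of clusters: E[m] = Σ R_d ρ_d(3.20), d = 0 to 3, for a t-field with 75 df. R_d are the resel counts of the search volume (R_3 = V/FWHM³).
2. Mean cluster size: (0.001 × V/voxel volume) ÷ (three-dimensional term of E[m]).
3. P(size ≥ k) = exp(−β k^(2/3)), with β = (Γ(5/2)/mean size)^(2/3) and Γ(5/2) = 1.329.
4. Family-wise error = 1 − exp(−E[m] × P(size ≥ 10)).

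**Worked case, 3 mm voxels, 8 mm FWHM.** E[m] = 29.75, of which the three-dimensional term is 27.24. Voxels expected above threshold: 0.001 × 1,500,000/27 = 55.56. Mean size: 55.56/27.24 = 2.04 voxels. β = (1.329/2.04)^(2/3) = 0.752. P(size ≥ 10) = exp(−0.752 × 4.642) = 0.0305. Expected false clusters: 29.75 × 0.0305 = 0.91. Error = 1 − exp(−0.91) = 0.60.

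**Worked case, 4 mm voxels, 10 mm FWHM.** E[m] = 15.57; mean size 23.44/13.95 = 1.68; β = 0.855; P(size ≥ 10) = 0.0189; expected false clusters 0.294; error 0.25.

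**One search, one direction, 1.5 litres.** The simulations are null Gaussian fields and full two-sample t-fields (39 v 38 assumed), with 18-neighbour clusters and from 8 to 1,500 maps per setting.

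| Voxel | FWHM | Random field | Simulations |
|---|---|---|---|
| 2 mm | 8 mm | 0.998 | 1.00 |
| 2 mm | 10 mm | 0.997 | 0.99 |
| 2 mm | 12 mm | 0.990 | 0.98 to 0.99 |
| 2 mm | 14 mm | 0.97 | – |
| 3 mm | 8 mm | 0.60 | 0.50 to 0.62 |
| 3 mm | 10 mm | 0.81 | 0.81 |
| 3 mm | 12 mm | 0.86 | 0.82 to 0.90 |
| 4 mm | 8 mm | 0.058 | 0.034 to 0.04 |
| 4 mm | 10 mm | 0.25 | 0.22 to 0.23 |
| 4 mm | 12 mm | 0.44 | – |
| 4 mm | 14 mm | 0.54 | – |

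The 0.50 at 3 mm and 8 mm comes from only 60 maps (SE about 0.06); 800 maps gave 0.57. The one-direction error crosses one half at a voxel size of about 3.1 mm for 8 mm FWHM and about 3.9 mm for 12 mm.

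**Search volume.** Over 1.2 to 1.8 litres the one-direction range is 0.94 to 0.999 at 2 mm and 0.52 to 0.90 at 3 mm. A 0.8-litre, grey-matter-only mask gives 0.39 to 0.66 at 3 mm.

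**Sidedness.** If .001 applies in each direction, the 3 mm random field range becomes 0.84 to 0.98. At 4 mm and 10 mm FWHM, 23% per direction gives 1 − 0.77² = 41%; direct simulation gives 38 to 43%. If .001 is two-sided in total, 3 mm and 8 mm FWHM falls to 0.48 by random field, with the larger simulations at 0.44 (800 maps) and 0.545 (400 maps).

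**Two tasks.** Treated as independent, 1 − (1 − p)²: 0.60 becomes 0.84 and 0.86 becomes 0.98 at 3 mm; 0.44 becomes 0.69 at 4 mm and 12 mm FWHM.

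**Extent needed for 5%, one direction.** About 84, 139 and 207 voxels at 2 mm, and 25, 41 and 62 voxels at 3 mm, for 8, 10 and 12 mm FWHM.

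**The case against.** The strongest reply is that the size of the problem turns on inputs the documents do not give. The only smoothness they state is the 8 mm kernel. With 4 mm voxels and effective smoothness no larger than that, 1,500 simulated t-field maps gave 3.4% in one direction, 6.7% in either direction and 1.7% for a two-sided .001 test. There the 10-voxel rule comes close to 5% control by itself. This stands, and it is why only a range can be given. It does not rescue the rule: nothing in the plan shows that this favourable case applies, and even there, both directions and both tasks treated as independent give 1 − 0.933² = 13%.

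The second reply is that little rests on these maps. The prior hypotheses are tested in the corrected ROI analyses, the whole-brain search comes second, and Results for primary outcomes reports no whole-brain finding. This also stands and limits the severity.

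The third is that cluster-level correction is one choice among several. That is fair: another family-wise method, or a plain exploratory label with no regional claim, would also answer the point.

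Two stronger inferences are not supported. A reader might conclude that naming a region is the expected outcome whenever the drug does nothing. That follows at 2 mm and in most 3 mm settings, but not for a single search at 4 mm with smoothness up to 12 mm. With 10 mm smoothness, counting both directions still gives only about 40%, and it cannot exceed 2 × 23% = 46%. A reader might also conclude that the reported ROI results are undermined; they do not depend on this threshold.

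**Conclusion.** The concern holds in a conditional form. The whole-brain threshold has no stated family-wise correction and no exploratory label, and whether 10 voxels protects against false clusters depends on settings that the plan leaves open. For one search in one direction the risk is near certain at 2 mm voxels. At 3 mm it is generally more likely than not, and close to even, roughly 45 to 50%, if smoothness is only 8 mm and .001 is two-sided in total. At 4 mm it lies between about nominal and somewhat under one half for smoothness of 8 to 12 mm. All of this assumes no true effect anywhere, a volume of about 1.5 litres and the stated smoothness range. The consequence is confined to regions outside the predicted ROIs, so this is a modest but worthwhile correction.

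**What to change.** Keep p < .001 as the cluster-forming threshold. Declare a region beyond the ROIs only at cluster-level family-wise p < .05, with alpha split across the two directions (0.025 each); an equivalent family-wise method is acceptable. Label any map shown at p < .001 with 10 voxels as exploratory and uncorrected, and attach no regional drug-effect claim to it. State the voxel size, search mask, estimated smoothness, sidedness and the contrasts searched. Also say whether the 5% applies per task or across both, since 5% per task allows 1 − 0.95² = 9.75% over two independent searches.

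Because results already exist, this means re-thresholding or relabelling any whole-brain maps already produced, and recording that the change came after analysis. The planned SPM8 analysis already reports cluster-level values, so no new data are needed. The cost is fewer exploratory regions to report; the ROI tests are unaffected.

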## Study Design & Methods

Overview: To assess the role of opioids in the experience of connecting with others, an opioid antagonist, naltrexone, will be administered in a randomized, double-blinded, placebo controlled design. Participants will attend a baseline session where they will complete trait measures in order to obtain baseline measures in feelings of connection. Participants will then be scheduled for an fMRI scan where they will be randomly assigned to a drug condition (naltrexone or placebo). During the scan, participants will complete a number of tasks designed to elicit feelings of social connection. After the scan, participants will complete self-report measures in order to assess the effect of opioid antagonism on perceptions of their social relationships.

Timeline and anticipated duration of study procedures:

1. Telephone Screening (15 minutes)
2. In-person visit #1 (Sennott Square): review and sign consent form, baseline questionnaires (60 minutes)
3. In-person visit #2 (Neuroscience Imaging Center): Experimental Session at fMRI scanner (3 hours)
  - 3a. Assignment to study drug, wait for peak effects (60 minutes)
  - 3b. fMRI scan (60 minutes)
  - 3c. post scan assessments and video recording (60 minutes)

Total time: 4 hours

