### IN-PERSON BASELINE VISIT #1:

Participants will review the consent form and be allowed to ask clarifications before giving consent to participate. Participants will then answer questions about their perceptions of their

social relationships, feelings over the past 24 hours, general health and health-related behaviors, and demographics. In addition, participants will be asked to complete a number of personality measures to establish a baseline for social interactions and feelings about relationships.

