#### IN-PERSON VISIT #2:

On the day of the study, participants will arrive at the Magnetic Resonance Research Center (MRRC) where they will complete a urine drug test to test for the presence of opiates and other drugs, a urine pregnancy test (if female) and complete a baseline physical symptoms checklist. A positive urine test for either drugs or pregnancy will result in the withdrawal of the participant from the study.

To ensure safety for an MRI scan, participants will undergo a two-step safety screening procedure with the MRI technician. First, a written screening form is completed during a face-to-face interview with the participant and the technologist. Once the participant has passed the written screening, then visual screening is performed by the technologist to identify and eliminate any contraindicated objects on the participant's body or clothing. Participants will then be randomly assigned to receive either 50mg of oral naltrexone or placebo.

Details on drug randomization and study drug blind methods: (1) Randomization: An individual unassociated with the main study will randomly assign participants to drug A or drug B on the day of the scheduled scanning session by using a block randomization method. This will ensure that there are equal numbers of men and women assigned to each drug condition. This individual will not have access to any of the data or any information about the participant except for their gender and age. It will be necessary for the person in charge of randomization to know the gender and age of the participant so that they may keep the two conditions balanced. (2) Study Drug Blind: The PI ([name]), study coordinator, any trained research assistant's, and the participants will all be blinded during the study, thereby maintaining the double-blind. Only the study physician, [name], and the individual who performs the randomization will be unblinded. The PI will be told which drug is A and which is B at the end of data collection. Finally, the drug and placebo will be packaged into identical capsules so that the pills look identical to the experimenters.

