#### **POST SCAN ASSESSMENTS:**

Outside of the scanner, participants will rate their feelings of connection (e.g. “How connected did reading the messages make you feel?”, “How warm did reading the messages make you feel?”, “How touched did reading the messages make you feel?”) to reading each set of messages. They will also complete the same physical symptoms checklist that they completed prior to taking the study drug and their perceptions of their close other from the picture task.

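### Self-reported connection is compared by unadjusted t-tests although Visit 1 baseline measures and the factors balanced at allocation are available: a valid analysis that may give up precision

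*Combined protocol and SAP*

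**What the plan says.** The primary outcomes are "Neural activity and self-reported feelings of connection in response to the messages task and the picture-viewing task" (Statistical Considerations).

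Three design features bear on how the arms are compared:

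- **Baseline.** The overview in Study Design & Methods has participants "complete trait measures in order to obtain baseline measures in feelings of connection". The Visit 1 section adds that they "complete a number of personality measures to establish a baseline for social interactions and feelings about relationships".
- **Allocation.** Visit 2 uses block randomization: "This will ensure that there are equal numbers of men and women assigned to each drug condition". The person who randomizes must also "know the gender and age of the participant so that they may keep the two conditions balanced".
- **Outcome timing.** After the scan, "participants will rate their feelings of connection" for each set of messages. No pre-drug rating on the same items is described.

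The self-report analysis is then: "on self-reported feelings of connection in response to the scanner tasks, we will conduct independent samples t-tests". For the ROIs, activity "will be examined to see if average neural activity in these regions differs between naltrexone and placebo participants". The whole-brain analysis is described as a between-group comparison. Statistical Considerations gives no role to the baseline measures, sex or age in any of these.

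The results section reports the messages-task ROI drug tests as t(75), and a self-report effect for the messages task in the expected direction with p > .10.

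**The concern.** A baseline measure of the construct behind the self-report outcome is collected before randomization, and the arms are deliberately balanced on sex and age. The stated test uses none of this.

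There are two separate costs:

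- Outcome variance that the Visit 1 score could explain stays in the error term. The design is between-subject with a single post-scan assessment, so stable differences between people are not otherwise removed from a raw rating.
- Balancing removes a factor's contribution from the difference between arms, but an unadjusted test leaves that contribution in the standard error. The standard error is then too large, and the test conservative, to the extent that the factor predicts the outcome.

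At stake is how sharply the trial can estimate the drug effect on self-reported connection, which was reported as not significant.

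**Working it through.** **1. Do the reported tests look unadjusted?** The close-other versus stranger tests have 76 degrees of freedom, so N = 76 + 1 = 77. A two-sample test without covariates has 77 − 2 = 75, as reported for the drug effect on the ROIs. One covariate would give 74; a baseline score, sex and age would give 72. This is evidence for the messages-task ROIs only.

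As a check on the figures, t = 1.859 and 2.198 on 75 df give one-sided p of 0.0335 and 0.0155, which match the reported .034 and .016 to within rounding of t. The two-sided values are 0.067 and 0.031. Sidedness is a separate matter; the power figures below are two-sided.

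**2. Inputs for the precision calculation.**

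- N = 77, from the degrees of freedom. Arm sizes are not given, so a 38/39 split is assumed.
- Two-sided alpha of 0.05, assumed.
- Standardized difference d = 0.42, assumed. The documents give no planned effect. The value equals the observed left-ROI effect: 1.859 × √(1/38 + 1/39) = 1.859 × 0.2279 = 0.424. It is borrowed from a neural outcome and is not an estimate for self-report.
- R, the multiple correlation of the covariates with the outcome. It is not given, so a range is shown.

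**3. Formulas.** Residual variance factor = 1 − R². Standard error ratio = √(1 − R²). Equivalent unadjusted N = 77/(1 − R²). Power is from the noncentral t with noncentrality d / √[(1 − R²)(1/38 + 1/39)].

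Unadjusted, the noncentrality is 0.42/0.2279 = 1.843, with critical value 1.992 on 75 df; power is 44.4%. Adjusted, with 73 df (two covariates) or 72 df (three), the results agree to the rounding shown:

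| R | SE ratio | Equivalent N | Power at d = 0.42 |
|---|---|---|---|
| unadjusted | 1.00 | 77 | 44% |
| .1 | 0.995 | 78 | 45% |
| .2 | 0.98 | 80 | 46% |
| .3 | 0.95 | 85 | 48% |
| .5 | 0.87 | 103 | 56% |
| .6 | 0.80 | 120 | 62% |

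At R = 0 with three covariates power is 44.36% against 44.39% unadjusted, so the lost degrees of freedom cost about 0.03 percentage points. The formula treats the covariates as balanced between arms. Chance imbalance in the Visit 1 score would trim the gain slightly, so at R near .1 there may be none.

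**4. Sensitivity to d.** At d = 0.5, power is 58% unadjusted and 60%, 62% and 71% at R = .2, .3 and .5. At d = 0.2, it is 14% unadjusted and 15% and 17% at R = .3 and .5.

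**5. Conservatism from ignoring a balanced factor.** If a balanced factor explains a share s of outcome variance, the nominal 5% test has actual size of about 2 × P(t > 1.992/√(1 − s)). For s = 1%, 5%, 10% and 20% this is about 4.9%, 4.5%, 3.9% and 2.9%. It applies to the balancing factors, not to the Visit 1 score, on which allocation was not balanced.

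**The case against.** The strongest reply is that nothing here is an error. Leaving covariates out does not bias a randomized comparison, and leaving out a balanced factor errs on the cautious side. That stands: the point is about efficiency.

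The benefit may also be small. The baseline is a set of trait and personality measures taken at an earlier visit, whereas the outcome is a task-specific rating made after the scan. R could well be low, and below about .2 the gain is trivial. That stands too, and is why the table starts at .1. For neural activity, the planned within-person contrasts already remove some stable variation between people, and no baseline scan is described.

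Three stronger readings are tempting, and the documents do not support them:

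- *Every drug comparison is specified as an unadjusted two-sample test.* The t-test is stated only for self-report. For the messages-task ROIs the unadjusted form is inferred from the degrees of freedom. For the whole-brain analysis it rests on no covariate being named.
- *Trait differences in connection are the main source of noise.* No standard deviation, variance component or correlation is given.
- *Adjustment would have turned the self-report result positive.* That result is reported only as p > .10, for the messages task alone, without an estimate. If the true effect were as small as d = 0.2, adjustment would change little.

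**Conclusion.** The point holds as a low-cost improvement in precision. The plan collects baseline connection measures and balances on sex and age, then compares self-reported connection without using them. Under the assumptions above (77 people split 38/39, two-sided 5%, d = 0.42), power would rise by about 1 to 4 percentage points at R of .1 to .3, and by about 11 to 18 points at R of .5 to .6. The omission is certain for self-report; the size of the gain is not, because R is unknown. The analysis as planned remains valid, and the reported self-report result should not be called wrong on this ground.

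**What to change.** - **Self-report.** Specify a linear model of post-scan feelings of connection on drug, one named Visit 1 connection score, sex and age. Report the adjusted difference with a 95% confidence interval. Several measures are collected at Visit 1, and the plan does not say how the post-scan ratings form one outcome. Both the score and the outcome must therefore be named, with the reason for each choice, before the model is fitted.
- **ROI and whole-brain.** Fit drug plus the allocation factors, sex and age. No baseline neural measure is available to add.
- **Status.** Results are already reported, so the adjusted analyses should be labelled post hoc and supplementary and shown beside the planned t-test, not in place of it. In a future trial the adjusted model can be specified as primary from the start.

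The cost is two degrees of freedom for the neural models and three for self-report, plus a short addition to the analysis text. The plan already provides for collecting the data, and no study procedure changes.
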